### **Introduction:**

CO2 measurements obtained using different methodologies are used as a marker for ventilatory status in various clinical settings. Accuracy of CO2 measurements is especially important in cystic fibrosis patients. During procedures requiring general anesthesia, CO2 is monitored through the endotracheal tube (EtCO2) and/or arterial blood gas (ABG) and anesthesia adjusted to maintain healthy CO2 levels. Outside of the operating room, fingerstick capillary (CapCO2) or transcutaneous (TCO2) are used to manage other treatments in cystic fibrosis patients. Unfortunately, there are very little data in the literature to compare and contrast accuracy of the differing methodologies. Comparative studies are needed to identify the most accurate method for measuring CO2 in various settings. This study will obtain CO2 measurements simultaneously using four different methodologies (EtCO2, ABG, CapCO2, and TCO2) in cystic fibrosis patients undergoing general anesthesia.

### **Primary Objectives:**

1. Validate the use of EtCO2 monitoring of cystic fibrosis patients during general anesthesia.
2. Compare the results of EtCO2 with CapCO2, TCO2 and ABG in CF patients undergoing general anesthesia.

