### **Secondary Objective:**

1. Stratify CF patients based on FEV1 and genotype to determine if discrepancies between EtCO2, CapCO2, TCO2, and ABG change based on level and type of disease. This comparative study will use data FEV1 and genotype data collected through separate chart review.

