### **Study Population:**

All patients that have a confirmed diagnosis of cystic fibrosis (positive sweat chloride value  $\geq 60$  mEq/L) and/or genotype with two identifiable mutations consistent with CF, accompanied by one or more clinical features consistent with the CF phenotype) and are hemodynamically stable undergoing general anesthesia for a scheduled procedure will be approached and asked to participate in the study. Patients undergoing emergency procedures will not be included in the study. Patients meeting the criteria for participation will be identified during their CF clinic visit or during an inpatient stay.

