### **Procedures:**

1. When a patient is scheduled for a procedure requiring general anesthesia, a secure message will be sent to [name], [name], [name], and [name] with patient identification, date and time of procedure.

2. Just prior to the procedure, an anesthesia research nurse will obtain informed consent/assent for the study.
3. After anesthesia induction, simultaneous EtCO2, ABG, TCO2, and CapCO2 will be measured and results entered on a data form attached to the signed consent.
4. The research nurse will place the signed consent form and the data form in a locked file cabinet in anesthesia.
5. [name] from Pulmonary Medicine will pick up the documents from anesthesia and enter the information into the password-protected study database. No patient identifiers will be entered into the database.

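### Must the plan fix a reference method, acceptance limit and sample size before it can claim to validate EtCO2?

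*Combined protocol and SAP*

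**What the plan says.** Under Primary Objectives, item 1 is to "Validate the use of EtCO2 monitoring of cystic fibrosis patients during general anesthesia" and item 2 is to "Compare the results of EtCO2 with CapCO2, TCO2 and ABG in CF patients undergoing general anesthesia". The Secondary Objective asks whether differences between the methods vary with disease, in the words "determine if discrepancies between EtCO2, CapCO2, TCO2, and ABG change based on level and type of disease".

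The Introduction describes practice under general anesthesia: "CO2 is monitored through the endotracheal tube (EtCO2) and/or arterial blood gas (ABG) and anesthesia adjusted to maintain healthy CO2 levels". It places capillary and transcutaneous readings outside the operating room. It also says that "there are very little data in the literature to compare and contrast accuracy of the differing methodologies" and that "Comparative studies are needed to identify the most accurate method for measuring CO2 in various settings".

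The Study Population section says that eligible patients "will be approached and asked to participate in the study" and gives no target number. Procedures, item 3, sets the measurement step ("After anesthesia induction, simultaneous" readings by all four methods). The remaining items deal with storing forms and entering data. There is no analysis section.

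**The concern.** To validate a method sounds like reaching a verdict. A verdict needs a standard to compare against, a measure of how far apart two methods are, a limit on how far apart they may be, and enough patients to tell. None of the four is written down. ABG is the natural standard, since it is the only other method the Introduction places in the operating room, but item 2 lists it beside the capillary and transcutaneous methods without singling it out.

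Even if analysts take ABG as the reference and report bias and limits of agreement, they hold an estimate and not yet a pass or a fail. Someone must then say how wide is too wide. If that is settled after the data are seen, the same readings could be published as validated or not validated, and readers would assume that EtCO2 had passed a test set in advance.

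**Working it through.** The plan states no SD, margin, error rate or sample size, so it has no figure to reproduce. Every number below rests on assumed inputs in mmHg and shows what could happen, not what is likely.

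**1. Does the verdict depend on the limit?** The 95% limits of agreement are bias ± 1.96 × SD of the paired differences (EtCO2 minus ABG). Call it a pass if both lie within ±L. For bias -2 and SD 3: -2 ± 1.96 × 3 = -2 ± 5.88, so -7.88 to 3.88. That fails at L = 5 and 7.5 and passes at L = 10. The larger absolute limit, |bias| + 1.96 × SD, decides each case:

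| Bias | SD 2 | SD 3 | SD 4 | SD 5 |
|---|---|---|---|---|
| 0 | 3.92 | 5.88 | 7.84 | 9.80 |
| -2 | 5.92 | 7.88 | 9.84 | 11.80 |
| -4 | 7.92 | 9.88 | 11.84 | 13.80 |

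One cell passes at all three limits (3.92), three fail at all three (11.80, 11.84, 13.80), and 8 of 12 change verdict between L = 5 and L = 10.

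**2. With sampling error.** Differences are simulated as normal, with a pass if |mean| + 1.96 SD ≤ L. At n = 20 and a bias of size 2, the share of studies whose verdict differs between L = 8 and L = 12 is 43, 80, 55, 23 and 7% at SD 3, 4, 5, 6 and 7. Over n = 10 to 30, bias 0 to 4 and SD 3 to 7, it runs from 0.4% (n = 30, bias 4, SD 7) to 96% (n = 30, bias 4, SD 3). It is small where nearly every study passes both limits or fails both.

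**3. Does the number of patients matter?** The 95% confidence half-width of a limit is t(0.975, n-1) × SD × √(1/n + 1.96²/(2(n-1))). This is 1.27, 0.81, 0.65 and 0.49 SD at n = 10, 20, 30 and 50. For bias -2 and SD 3 the outer bound of the lower limit is -(7.88 + 0.814 × 3) = -10.32 at n = 20 and -(7.88 + 0.645 × 3) = -9.82 at n = 30. If that bound had to lie within ±10, the first would fail and the second pass.

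**4. Could a useful sample size be written now?** Take L = 10, require only that the point limits lie inside, and ask for an 80% chance of passing. About 13 patients are needed at SD 4 with bias 0, about 1,270 at SD 4 with bias 2, and about 2,650 at SD 5 with bias 0. If the confidence intervals of the limits must also lie inside, SD 4 with bias 0 needs about 108. Without an SD from somewhere, a stated number would be a guess.

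**5. What does the text point to?** The readings are simultaneous, so the data are paired. Item 2 speaks of comparing results and the Secondary Objective of discrepancies. Both lead to paired differences, and bias with limits of agreement is the standard summary of those.

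**The case for a change.** The strongest case for a change is that an estimate answers item 2 but cannot on its own answer item 1. It adds that nothing in the text excludes a poor criterion. At n = 20, bias 2 and SD of differences 3, 5 and 7, calling EtCO2 valid when a paired t-test is non-significant would pass 19, 60 and 77% of studies, so the noisier method does better. Limits of agreement within ±10 would pass 97, 19 and 1%. Writing down a reference and an analysis would also be cheap.

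Part of this stands. The four items are absent, and a published claim of validation would be only as good as the criterion behind it. But the t-test rule is one the plan nowhere suggests, and the wording points away from it. A yes/no declaration is one reading of item 1; no section commits to announcing a pass or fail.

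Two supporting arguments fail:

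- It is tempting to say that adjusting anesthesia narrows the CO2 range and so makes correlation or a paired test especially misleading. The simulation goes the other way for correlation. With SD of differences 7, a significant correlation passes about 64% of studies at a between-patient SD of 4 and 98% at 8. The paired test uses only the differences, so the range does not affect it.
- The shortage of literature on accuracy does not leave investigators without a limit. How much error is tolerable is a clinical judgement and need not come from studies comparing methods.

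Nor is a rewrite free of side effects. Ranking EtCO2-ABG above the other two pairs would demote comparisons that item 2 lists as primary, side by side.

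**Conclusion.** No change follows. This is missing detail that analysts would fill sensibly, not an error in anything the plan states. There is no wrong rule, contradictory passage or miscalculated number to correct. The paired readings support the expected analysis whether or not it is written down. Bias and limits of agreement with confidence intervals let any reader apply a limit of their own, and the intervals would show openly if too few patients had been recruited.

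An amendment could only ask the investigators to supply their own reference, limit, pass rule and sample size. The documents offer no inputs from which to check or derive any of these.

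What remains is a risk about the word used in the report: read as a pass/fail verdict, it could turn on a limit chosen later. The documents do not say when a limit would be chosen, or whether one would be. The range of 0.4% to 96% rests wholly on assumed biases, SDs, sample sizes and limits, so it shows that the risk can exist and does not measure it. The conclusion assumes that the analysts use ABG as the reference for item 1 and report agreement as paired differences, which is how the Introduction and the Procedures most naturally read.

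### Primary Objective 2 compares CapCO2 and TCO2 only with EtCO2, the method under validation, and no reference is named, so their spread against ABG is not a primary result

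*Combined protocol and SAP*

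**What the plan says.** The Primary Objectives section has two items. Item 1 is "Validate the use of EtCO2 monitoring of cystic fibrosis patients during general anesthesia". It does not say what EtCO2 is to be validated against. Item 2 is "Compare the results of EtCO2 with CapCO2, TCO2 and ABG in CF patients undergoing general anesthesia".

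The Introduction gives the reason for the study. It says that "there are very little data in the literature to compare and contrast accuracy of the differing methodologies", and then that "Comparative studies are needed to identify the most accurate method for measuring CO2 in various settings". It presents this study as the response: "This study will obtain CO2 measurements simultaneously using four different methodologies (EtCO2, ABG, CapCO2, and TCO2) in cystic fibrosis patients undergoing general anesthesia". ABG appears there as one of two ways of monitoring CO2 under anesthesia, beside EtCO2, and is not called a reference.

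The Secondary Objective stratifies by FEV1 and genotype to "determine if discrepancies between EtCO2, CapCO2, TCO2, and ABG change based on level and type of disease". Procedures, item 3, has all four values taken together: "After anesthesia induction, simultaneous EtCO 2 , ABG, TCO 2 , and CapCO 2 will be measured and results entered on a data form".

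No section from the Introduction to the Procedures designates ABG, or any other method, as the reference. The opening pages were not in the text reviewed, so the absence is judged on those sections.

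**The concern.** Accuracy is a statement about distance from a reference. The stated motivation is to find the most accurate method, yet the primary comparisons set CapCO2 and TCO2 only against a method whose own validity is the subject of Objective 1. An EtCO2-CapCO2 difference contains the errors of both methods, so its spread does not describe CapCO2.

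A report that followed Objective 2 to the letter would give limits of agreement for CapCO2 and TCO2 against EtCO2 and none against arterial CO2. Those limits could be wider or narrower than the ones the rationale calls for. A reader of the report could not convert one set into the other.

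**Working it through.** **Which pairs are named.** Four methods give 4 × 3 / 2 = 6 pairs. Objective 2 names three: EtCO2-CapCO2, EtCO2-TCO2 and EtCO2-ABG. The three not named are CapCO2-ABG, TCO2-ABG and CapCO2-TCO2.

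**What the three named pairs can deliver.** Within a patient,

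CapCO2 − ABG = (EtCO2 − ABG) − (EtCO2 − CapCO2).

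- *Mean bias.* Means subtract. If the same patients contribute to all pairs, mean CapCO2-ABG bias is the mean EtCO2-ABG difference minus the mean EtCO2-CapCO2 difference. The same holds for TCO2.
- *Spread.* Var(CapCO2 − ABG) = Var(EtCO2 − ABG) + Var(EtCO2 − CapCO2) − 2 Cov(EtCO2 − ABG, EtCO2 − CapCO2). The covariance is not part of a pair-by-pair summary, so the limits of agreement need the patient-level CapCO2-ABG differences.

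**How far apart the two sets of limits could be.** The documents give no SD, correlation or number of patients. Every input below is an assumption, and there is no figure in the plan to reproduce. Let sE be the SD of EtCO2-ABG, sC the SD of CapCO2-ABG, and r the correlation between these two differences. Then

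SD(EtCO2 − CapCO2) = √(sE² + sC² − 2·r·sE·sC), and limits of agreement = ±1.96 × SD about the mean.

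Take sE = 4 and sC = 2.5 mmHg. The CapCO2-ABG limits are 1.96 × 2.5 = ±4.9.

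If r = 0, the EtCO2-CapCO2 limits are 1.96 × √(16 + 6.25) = 1.96 × 4.717 = ±9.2, which is 1.89 times as wide.

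Zero correlation in effect takes ABG as free of error, because any ABG error enters both differences. If ABG error has SD e and errors are otherwise independent, the covariance is e² and the variance becomes 22.25 − 2e²:

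| Assumed ABG error SD (mmHg) | SD of EtCO2-CapCO2 | Limits (mmHg) | Ratio to ±4.9 |
|---|---|---|---|
| 0 | √22.25 = 4.72 | ±9.2 | 1.89 |
| 1 | √20.25 = 4.50 | ±8.8 | 1.80 |
| 1.5 | √17.75 = 4.21 | ±8.3 | 1.69 |
| 2 | √14.25 = 3.77 | ±7.4 | 1.51 |

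**Range over other assumptions.** With sE of 2, 4 or 6 and sC of 1.5, 2.5 or 4 mmHg, the ratio of EtCO2-CapCO2 limits to CapCO2-ABG limits is:

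- 1.24 to 4.40 at r = −0.3
- 1.12 to 4.12 at r = 0
- 0.97 to 3.82 at r = 0.3
- 0.60 to 3.26 at r = 0.8

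The lowest value comes from sE = 2, sC = 2.5, r = 0.8: √(4 + 6.25 − 8) = 1.5, and 1.5 / 2.5 = 0.60. There CapCO2 would look tighter against EtCO2 than it is against ABG. In general the EtCO2-CapCO2 limits are the narrower ones when r exceeds sE / (2·sC). For the 4 and 2.5 case that threshold is 4 / 5 = 0.8.

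**The case against.** The strongest reply is that little is lost.

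- *EtCO2-ABG is already primary, and mean bias follows by subtraction.* This stands. A reader might infer that the primary comparisons say nothing about the accuracy of CapCO2 and TCO2. They do not support that: average bias against ABG is recoverable, and only the spread is not.
- *A shared bias would mislead no careful reader.* This also stands. One might infer that a method sharing EtCO2's bias would be ranked above one that tracks ABG. The plan nowhere proposes to treat closeness to EtCO2 as accuracy, and the EtCO2-ABG result required by Objective 2 would expose the bias.
- *The Secondary Objective covers the missing pairs.* In part. It lists all four methods without singling out EtCO2, and the discrepancies must be computed before anyone can ask whether they change. So it would be wrong to say that the plan leaves CapCO2-ABG and TCO2-ABG out altogether. But the question there is variation by FEV1 and genotype, so an overall primary statement is still missing.
- *EtCO2 as common comparator suits an objective about EtCO2.* This is fair. The Introduction contrasts monitoring in the operating room with CapCO2 and TCO2 outside it, and how EtCO2 relates to them is a legitimate question. It does not meet the Introduction's call to identify the most accurate method.
- *Item 2 may have meant every pair.* The sentence does not say so. If that was the intent, one line of wording settles it.
- *The numbers are all assumed.* True. The range from 0.60 to 4.40 shows that the inputs decide the answer, so the arithmetic shows that the two sets of limits are not interchangeable and no more than that.

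**Conclusion.** The point holds in a limited form. Objective 2 compares CapCO2 and TCO2 only with the method under validation, no reference method is named, and CapCO2-ABG and TCO2-ABG are not primary comparisons. What is lost is their overall limits of agreement against ABG. Their mean bias is not lost, provided the same patients contribute to every pair.

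Under the assumed SDs of 4 and 2.5 mmHg, the reported limits for CapCO2 would be about 1.5 to 1.9 times those against ABG, for an ABG error SD between 2 and 0. Under other assumptions the direction can reverse. Confidence is high in the textual gap and moderate in the size of its consequences, since no document figure supports the inputs. This is a cheap improvement and does not undermine the study: the simultaneous values will exist, and nothing in the plan forbids the direct comparison.

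**What to change.** In Objective 2:

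1. Name the simultaneous ABG PaCO2 as the reference.
2. Add CapCO2-ABG and TCO2-ABG beside EtCO2-ABG as primary comparisons.
3. Report each of the three as mean bias and 95% limits of agreement, with confidence intervals for both.
4. Keep EtCO2-CapCO2 and EtCO2-TCO2 as descriptive comparisons.

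The cost is a change of wording and two more pairwise summaries. No new measurement is needed, because all four values are already planned together. The real commitment is to ABG as reference. The documents do not state it, the sponsor would have to accept it, and ABG's own measurement error would then count against each method.

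Precision depends on the number of patients, which is not given. For an assumed SD of 2.5 mmHg, the 95% confidence half-width of each limit, t(n−1) × SD × √(1/n + 1.96²/(2(n−1))), is about 2.0, 1.4 and 1.1 mmHg at assumed n of 20, 40 and 60.

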### **Secondary Objective:**

1. Stratify CF patients based on FEV1 and genotype to determine if discrepancies between EtCO2, CapCO2, TCO2, and ABG change based on level and type of disease. This comparative study will use data FEV1 and genotype data collected through separate chart review.

### **Study Population:**

All patients that have a confirmed diagnosis of cystic fibrosis (positive sweat chloride value  $\geq 60$  mEq/L) and/or genotype with two identifiable mutations consistent with CF, accompanied by one or more clinical features consistent with the CF phenotype) and are hemodynamically stable undergoing general anesthesia for a scheduled procedure will be approached and asked to participate in the study. Patients undergoing emergency procedures will not be included in the study. Patients meeting the criteria for participation will be identified during their CF clinic visit or during an inpatient stay.

### **Procedures:**

1. When a patient is scheduled for a procedure requiring general anesthesia, a secure message will be sent to [name], [name], [name], and [name] with patient identification, date and time of procedure.

2. Just prior to the procedure, an anesthesia research nurse will obtain informed consent/assent for the study.
3. After anesthesia induction, simultaneous EtCO2, ABG, TCO2, and CapCO2 will be measured and results entered on a data form attached to the signed consent.
4. The research nurse will place the signed consent form and the data form in a locked file cabinet in anesthesia.
5. [name] from Pulmonary Medicine will pick up the documents from anesthesia and enter the information into the password-protected study database. No patient identifiers will be entered into the database.

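### Does validating EtCO2 monitoring need more than one simultaneous set of readings per patient?

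*Combined protocol and SAP*

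**What the plan says.** Primary Objective 1 is to "Validate the use of EtCO2 monitoring of cystic fibrosis patients during general anesthesia". Primary Objective 2 is to "Compare the results of EtCO2 with CapCO2, TCO2 and ABG in CF patients undergoing general anesthesia". The Introduction sets the clinical background: "CO2 is monitored through the endotracheal tube (EtCO2) and/or arterial blood gas (ABG) and anesthesia adjusted to maintain healthy CO2 levels". It gives the reason for the study as "Comparative studies are needed to identify the most accurate method for measuring CO2 in various settings".

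Measurement is described once, in Procedures item 3: "After anesthesia induction, simultaneous EtCO 2 , ABG, TCO 2 , and CapCO 2 will be measured", with "results entered on a data form attached to the signed consent". No repeat, interval, second time point or time after induction is given. The Introduction adds "This study will obtain CO2 measurements simultaneously using four different methodologies", but the plural there fits one reading from each of four methods as well as it fits several sets. The data form is not among the documents.

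**The concern.** Monitoring suggests use over time, and the Introduction describes anesthesia being adjusted to the CO2 level. The natural reading of Procedures item 3 is one set per patient. Each patient then contributes one EtCO2-minus-comparator difference per comparator. A stable patient offset and within-patient error are mixed in that difference, and adding patients does not separate them.

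At stake is the claim made under Objective 1. A report following its wording could say that EtCO2 is validated for following patients through an anesthetic, when the data support agreement at the sampled times only. The same limits of agreement are compatible with EtCO2 following a patient's CO2 well or poorly.

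**Working it through.** **Inputs.** The documents give no SD, agreement limit, sample size or number of sets, so there is no figure in the plan to reproduce. The SDs, variance shares, bias shift and patient numbers below are all assumptions.

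**Model.** Difference = bias + patient offset (SD σ_b) + within-patient error (SD σ_w).

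- One set per patient: SD = √(σ_b² + σ_w²), and the limits of agreement are bias ± 1.96 × SD.
- Change between two times in one patient: the offset cancels, so the limits are shift in bias ± 1.96 × √2 × σ_w = shift ± 2.772 × σ_w. This assumes independent errors and a constant SD.

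**What one set leaves open.** Take σ_w² as 19% or 81% of the total variance, with no shift (change limits use unrounded σ_w):

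| SD of differences (mmHg) | Limits of agreement | σ_w at 19% / 81% | Change limits at 19% / 81% |
|---|---|---|---|
| 3 | ±5.88 | 1.31 / 2.70 | ±3.62 / ±7.48 |
| 4 | ±7.84 | 1.74 / 3.60 | ±4.83 / ±9.98 |
| 5 | ±9.80 | 2.18 / 4.50 | ±6.04 / ±12.47 |

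Within each row the limits of agreement are the same, while the change limits differ about twofold (√(0.81/0.19) = 2.06). The statistical point is correct: one set per patient says nothing about tracking.

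**Can one set say anything about later in the anesthetic?** If every set is taken before a bias shift of 3 mmHg, the shift is invisible. In the SD 5, 19% case the change limits would be 3 ± 6.04, or −3.04 to 9.04 mmHg, with the limits of agreement still ±9.80. But Procedures item 3 fixes no minute or phase. If half the sets fell after the shift, the mean bias would move by 0.5 × 3 = 1.5 mmHg, and the SD would be √(25 + 0.25 × 9) = √27.25 = 5.22, giving limits of ±10.2. Single sets taken at varying times therefore carry some information between patients about time dependence. It is only within-patient change that they cannot address.

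**Do the stated aims need within-patient change?**

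- The Introduction applies the word monitored to EtCO2 and to arterial blood gas alike. An arterial gas is a discrete sample, so in this protocol's usage the word need not mean continuous tracking.
- A set taken after induction in an anesthetized patient is taken during general anesthesia.
- The Introduction's stated need is to find the most accurate method. Objective 2 is a comparison of readings. One set per patient serves both.
- Neither the objectives nor the Introduction names tracking of change.

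**What would more data buy?** One option is to record EtCO2 whenever the care team happens to draw a further arterial gas. With n such patients, two sets each and a common shift estimated (df = n − 1), the 95% interval for σ_w runs from √(df/χ²₀.₉₇₅) to √(df/χ²₀.₀₂₅) times its estimate. The shift has half-width t₀.₉₇₅ × √2 × σ_w / √n.

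| n | Interval for σ_w (× estimate) | Half-width for shift, σ_w 2.18 / 4.50 (mmHg) |
|---|---|---|
| 10 | 0.69 to 1.83 | 2.2 / 4.6 |
| 30 | 0.80 to 1.34 | 1.2 / 2.4 |

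With 10 patients, a 3 mmHg shift would be smaller than its own half-width in the 81% case. The documents do not say that further arterial gases will be drawn, how many patients would have one, or that the research nurse stays to record readings. Such patients would also be a clinically selected subset.

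**The case for a change.** The best argument for a change is that Objective 1 stands apart from Objective 2. Read as agreement, it largely repeats the EtCO2-against-ABG comparison in Objective 2; read as a claim about monitoring over time, one set does not support it. The number of sets is a basic design parameter, and stating it would cost one phrase.

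Part of this stands. The count and timing are not stated, and a conclusion about within-patient tracking would not be supported by single sets. But overlap between two objectives does no harm to an analysis, and the protocol makes no tracking claim. The feared harm is a sentence in a future report, to be judged against the data then reported. An unstated number is missing detail. It does not show that the design fails a stated aim.

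**Conclusion.** No change follows. If there is one set per patient, differences from different patients can be treated as independent, and the ordinary bias and limits of agreement are valid at the sampled post-induction times. If the forms hold several sets, that will be plain from the data, and an analyst would use limits of agreement that separate between-patient from within-patient variation. Either way the gap is filled sensibly without altering the plan, and the conclusion under Objective 1 should reach no further than the times sampled.

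The uncertainty about within-patient change could be large (±6.0 against ±12.5 mmHg at an assumed SD of 5), but it concerns a property the documents do not set out to measure. An added analysis of unscheduled arterial gases would have unknown yield in a selected subset, and its gain is debatable. This view rests on reading EtCO2 monitoring as the name of the method and general anesthesia as the setting, which the Introduction supports. It would be different if tracking of change were a stated aim.

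### Does keeping patient identifiers out of the database prevent the CO2 records from being joined to FEV1 and genotype?

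*Combined protocol and SAP*

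**What the plan says.** Three parts of the protocol bear on this point.

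- **Secondary Objective.** The task is to "Stratify CF patients based on FEV1 and genotype to determine if discrepancies between EtCO2, CapCO2, TCO2, and ABG change based on level and type of" the illness. The stratifying variables are not collected at the procedure: "This comparative study will use data FEV1 and genotype data collected through separate chart review".
- **Procedures, items 3 and 4.** The four CO2 measurements are taken after induction, with "results entered on a data form attached to the signed consent". Storage is then specified: "The research nurse will place the signed consent form and the data form in a locked file cabinet in anesthesia".
- **Procedures, item 5.** A member of Pulmonary Medicine "will pick up the documents from anesthesia and enter the information into the password-protected study database". The item ends with the rule at issue: "No patient identifiers will be entered into the database".

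In addition, item 1 has a secure message sent to named staff "with patient identification, date and time of procedure". The sections from Introduction to Procedures mention no study number, code, key or linkage step.

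**The concern.** The secondary question can be answered only at patient level: each set of CO2 discrepancies has to sit beside the right patient's FEV1 and genotype. The chart review is necessarily organised by patient. If the CO2 values are typed into a file with neither a name nor a code, and the chart-review data are held in another file, the two files have no variable in common.

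Two consequences would be feared. At worst, no row could be joined and the secondary objective would have no evaluable patients. Failing that, someone might reconstruct the match afterwards from indirect clues and pair some patients wrongly, which would weaken any association between disease severity or genotype and the disagreement among methods. An uncoded row would also be harder to trace back to its source form when checking transcription.

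**Working it through.** The plan states no figure on this point, so there is nothing to reproduce. The check is whether the text, taken literally, rules out the join.

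**1. What the rule covers.** Item 5 excludes patient identifiers from one place, the study database. It does not mention codes, a key held elsewhere, or what may be done before entry.

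**2. Where identity is held.** Item 3 attaches the CO2 form to the signed consent. Item 4 stores the two together. Item 5 passes both to the person doing the entry. That person therefore knows whose values they are when the row is created. Nothing in the text says that the form is later detached or destroyed.

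**3. Routes that obey item 5 and still permit the analysis.**

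- *Coded number.* Each participant gets a non-identifying number, written on the form, the database row and the chart-review extract, with the key kept outside the database.
- *Linkage at entry.* With the consent in hand, FEV1 and genotype are taken from the chart review and put in the same de-identified row. This works even for a strict reader who counts a study code as an identifier.
- *Recovery from paper.* If neither was done, a row can be compared with the retained forms on all four CO2 values together. The form leads to the consent, and the consent to the chart. Ambiguity would come mainly from ties or transcription errors.

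Since at least one permitted route exists, the Secondary Objective and item 5 are compatible. The text is silent on the method of linkage, but it does not contradict itself.

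**4. The mismatch argument.** Let f be the fraction of rows paired with the wrong patient. If the errors are random and unrelated to the variables, wrong pairs contribute no covariance on average, so

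expected slope = (1 − f) × true slope.

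The documents give no value of f. Taking a range purely as an assumption:

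| f | 1 − f | Attenuation |
|---|---|---|
| 0 | 1.00 | 0% |
| 0.10 | 0.90 | 10% |
| 0.20 | 0.80 | 20% |

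The formula is sound, but it needs a reason to expect f well above zero. None is given: no section proposes matching on dates or on CO2 values, and under the first two routes f is limited to ordinary clerical error.

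**5. Reach.** Both primary objectives compare CO2 methods with one another. All four values are on the same form and enter the same row, so no join is needed.

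**The case for a change.** The best case for a change is that feasible is not the same as written down. The protocol names two data sources, keeps identifiers out of the database and never says how the sources meet. Item 5 describes entering what is on the documents collected from anesthesia, and the chart review is called separate, so linkage at entry is an inference. Even where it is used, the row still has no code by which to audit it. One sentence and one extra field would settle the matter, at the small cost of describing the data as coded.

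Part of this stands. The linkage step is unwritten, and if the CO2 values are entered uncoded while the chart-review data stay in another file, the two electronic files share no key. Tracing a row to its form would then be less convenient, though still possible from the four values.

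It does not follow that the plan needs amending. Assigning study numbers and holding the key apart is routine data management, and the existing sentence already allows it. The amendment would record what a team would do anyway and would alter no estimate, comparison or conclusion.

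**Conclusion.** The concern does not hold as a defect of the plan. The rule on identifiers and the need for chart-review data can both be met as written, so there is no basis for saying that the secondary objective cannot be analysed or that it loses all its patients. The effect on the primary objectives is nil. The effect on the secondary objective is also nil provided that the team uses a study code or completes the row at entry. Attenuation of 10% or 20% would need mismatch rates that have no source in the documents.

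The conclusion rests on two assumptions: that the form and consent stay together at least until entry, as items 3 to 5 describe, and that a non-identifying code is not itself treated as a patient identifier. If the second fails, linkage at entry still serves. What remains is an unwritten working detail that those running the study can be expected to fill sensibly.
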